17.1.4 Publication Policy

No study results obtained under this Investigational Plan, nor any information provided to the Investigator for the purposes of performing the study, will be published or passed on to any third party without the consent of the sponsor. Investigators are obligated to follow the sponsor publication policy, which is outlined in the Clinical Trial Agreement.

17.1.5 IRB Information

The sponsor requests waiver of the requirements under 21 CFR part 812.35(b) for submitting certification of IRB approval to the FDA prior to the beginning the study at a particular center. In lieu of this requirement the sponsor will submit an IRB/Investigator list update in six month intervals.

17.2 Study Investigators

The Principal Investigator at each site is responsible for ensuring that the HALO Clinical Study is conducted according to the Clinical Trial Agreement and all amendments thereto, the Investigational Plan, any conditions of approval imposed by applicable regulatory authorities and/or the reviewing IRBs, and all applicable laws and regulations. All Investigators shall avoid improper influence on or inducement of subjects, the Sponsor, and other Investigators participating in or contributing to the clinical study.

Investigators are responsible for obtaining informed consent prior to enrolling any subject in the clinical study. If new information becomes available during the study that can significantly affect a subject's future health and medical care, or willingness to continue in the study, that information will also be provided to the subjects in written form.

17.2.1 Records

Records and reports pertaining to this study to ensure that they no longer need to be retained on-site.

17.2.2 Compliance

The sponsor will review and monitor Investigator compliance and determine if there is a need to secure compliance based on the severity and/or trends in non-compliance to

the signed Clinical Trial Agreement with Abbott (formerly St. Jude Medical), the Investigational Plan, the applicable regulations or any conditions of approval imposed by the reviewing IRB or FDA (21 CFR 812.46 (a)). Depending on the severity and/or trend in non-compliance, the Investigator may receive a formal warning or re-training through a site visit or conference call.

17.2.2.1 *Deviations to the Investigational Plan*

A deviation is used to describe a situation in which the Investigational Plan was not followed. Deviations may be identified at the site or by in-house sponsor personnel, and will be recorded on the Deviation CRF. The site is responsible for notifying their IRB and providing IRB notification to the sponsor, if applicable.

17.2.2.2 *Emergency Deviations from the Investigational Plan*

If a deviation from the Investigational Plan is necessary to protect the life or physical well-being of a subject in an emergency, the Investigator must notify the sponsor and the appropriate IRB within five (5) working days. For all other changes in, or deviations from the Investigational Plan, prior written approval from the sponsor and the IRB is required.

The FDA and IRB will be notified if the deviation affects the scientific soundness of the Investigational Plan.

17.2.2.3 *Informed Consent Compliance*

If the 15mm MHV is used without obtaining informed consent, the Investigator will report such use to the sponsor and the appropriate IRB within five (5) working days with an explanation of the circumstances of such use per 21 CFR 812.150(a)(5).

Informed consent deviations may include, but are not limited to:

- Failure to obtain consent from the subject's legally authorized representative
- Failure to obtain the signature of the subject's legally authorized representative
- Failure to obtain date (and time, if required) of signature of the subject's legally authorized representative
- Failure to obtain legally authorized representative initials on each page, if applicable
- Failure to obtain signature of person conducting the informed consent process
- Failure to obtain witness signature, if applicable
- Use of unapproved informed consent form
- Failure to obtain HIPAA Authorization, if applicable

17.2.3 Institutional Audits

The Investigator will permit study-related auditing and inspections of all study-related documents by the IRB, government regulatory agencies, and the sponsor. The Investigator will allocate time for these activities, allow access to all study-related documents and facilities, and provide adequate space to conduct these visits.

17.3 Institutional Review Board (IRB)

17.3.1 Responsibilities

All IRBs must comply with applicable IRB regulations (21 CFR part 50) and IDE regulations (21 CFR part 812) in reviewing and approving device investigations. An IRB shall safeguard the rights, safety, and well-being of all study subjects.

17.3.2 Composition

The IRB shall be composed of members meeting the minimum requirements set forth in 21 CFR 56.107.

17.3.3 Initial Approval

Prior to shipment of study valves, the sponsor will require documentation of IRB approval of the Investigational Plan and the ICF. The initial IRB approval and approved ICF will be filed in the site Regulatory Binder.

17.3.4 Annual Renewal

An IRB shall conduct continuing review of the clinical study at intervals appropriate to the degree of risk posed by the device, but not less than once per year (21 CFR 56.109). A copy of the IRB renewal will be sent to the sponsor and filed in the site Regulatory Binder.

Continuation of research after expiration of IRB approval is a violation of the regulations.

The following must be completed if the IRB fails to renew the study:

- Research activities must stop if the IRB has not renewed the continuation of the study.
- Study valves must be returned to the sponsor.
- No new subjects may be enrolled into the study, and enrolled subjects cannot be seen for follow-up according to the protocol, except under the following circumstance:

- The IRB may provide a written directive that subjects should still be seen for safety follow-up pending re-approval. Under this IRB directive, subjects should be seen for safety follow-up only, in order to assure subject safety and welfare is being overseen.
- If the Investigator is actively pursuing approval, the IRB may be flexible in permitting currently enrolled subjects to continue to be seen.
 - The sponsor will require documentation from the IRB of this decision.
 - Subjects will need to be informed that the IRB approval has lapsed, and adverse events will be reported to the IRB and the sponsor.

Appendix 3: CDC Growth Charts

Birth to 36 months: Boys
Length-for-age and Weight-for-age percentiles

NAME _____

RECORD # _____

[figure not shown]
Published May 30, 2000 (modified 4/20/01).
 SOURCE: Developed by the National Center for Health Statistics in collaboration with the National Center for Chronic Disease Prevention and Health Promotion (2000).
<http://www.cdc.gov/growthcharts>

Birth to 36 months: Boys
Length-for-age and Weight-for-age percentiles

NAME _____

RECORD # _____

[figure not shown]
Published May 30, 2000 (modified 4/20/01).
 SOURCE: Developed by the National Center for Health Statistics in collaboration with the National Center for Chronic Disease Prevention and Health Promotion (2000).
<http://www.cdc.gov/growthcharts>

2 to 20 years: Boys
Stature-for-age and Weight-for-age percentiles

NAME _____

RECORD # _____

Published May 30, 2000 (modified 11/21/00).
SOURCE: Developed by the National Center for Health Statistics in collaboration with the National Center for Chronic Disease Prevention and Health Promotion (2000).
<http://www.cdc.gov/growthcharts>

[figure not shown]

SAFER • HEALTHIER • PEOPLE™

2 to 20 years: Boys
Stature-for-age and Weight-for-age percentiles

NAME _____

RECORD # _____

[figure not shown]
Published May 30, 2000 (modified 11/21/00).
 SOURCE: Developed by the National Center for Health Statistics in collaboration with
 the National Center for Chronic Disease Prevention and Health Promotion (2000).
<http://www.cdc.gov/growthcharts>

Birth to 36 months: Girls
Length-for-age and Weight-for-age percentiles

NAME _____

RECORD # _____

[figure not shown]
Published May 30, 2000 (modified 4/20/01).
 SOURCE: Developed by the National Center for Health Statistics in collaboration with the National Center for Chronic Disease Prevention and Health Promotion (2000).
<http://www.cdc.gov/growthcharts>

Birth to 36 months: Girls
Length-for-age and Weight-for-age percentiles

NAME _____

RECORD # _____

[figure not shown]
Published May 30, 2000 (modified 4/20/01).
 SOURCE: Developed by the National Center for Health Statistics in collaboration with the National Center for Chronic Disease Prevention and Health Promotion (2000).
<http://www.cdc.gov/growthcharts>

2 to 20 years: Girls
Stature-for-age and Weight-for-age percentiles

NAME _____

RECORD # _____

Published May 30, 2000 (modified 11/21/00).
SOURCE: Developed by the National Center for Health Statistics in collaboration with
the National Center for Chronic Disease Prevention and Health Promotion (2000).
<http://www.odc.gov/growthcharts>

[figure not shown]

SAFER • HEALTHIER • PEOPLE™

2 to 20 years: Girls
Stature-for-age and Weight-for-age percentiles

NAME _____

RECORD # _____

Published May 30, 2000 (modified 11/21/00).
SOURCE: Developed by the National Center for Health Statistics in collaboration with
the National Center for Chronic Disease Prevention and Health Promotion (2000).
<http://www.cdc.gov/growthcharts>

Appendix 11: Adverse Event Definitions

Listed below are guidelines for uniform reporting of adverse events related to the study valve. The definitions and categorization of event types are consistent with those recommended by Akins *et al.*²⁵ The DSMB will review and adjudicate adverse events according to these reporting guidelines.

Death

All deaths will be reported and categorized as either 'valve related', 'other cardiac related', or 'other cause' as defined below.

Valve-Related:

Death due to any of the following events involving the study valve: structural valvular deterioration, nonstructural dysfunction, valve thrombosis, embolism, bleeding event, endocarditis, or reintervention. Sudden, unexplained deaths of which the cause or relationship has not been determined by clinical investigation or autopsy findings are considered valve related.

Other Cardiac:

Death resulting from cardiac causes, excluding valve-related death. Examples include congestive heart failure, acute myocardial infarction, and documented fatal arrhythmias.

Other Cause:

Death due to any cause, excluding valve-related mortality or other cardiac death.

Endocarditis

Any infection involving the study valve that is diagnosed according to Modified Duke Criteria²⁶ for endocarditis will be reported. Modified Duke Criteria are defined as follows:

1. Definite Infective Endocarditis

Definite infective endocarditis is defined by pathologic criteria or clinical criteria as defined below. The presence of both pathologic and clinical criteria is not necessary to meet the definition of definite infective endocarditis.

a. Pathologic Criteria

- i. Microorganisms demonstrated by culture or histologic examination of a vegetation, a vegetation that has embolized, or an intracardiac abscess specimen; or
 - ii. Pathologic lesions; vegetation or intracardiac abscess confirmed by histologic examination showing active endocarditis
 - b. Clinical Criteria
 - i. 2 major* criteria; or
 - ii. 1 major* criterion and 3 minor** criteria; or
 - iii. 5 minor** criteria
2. Possible Infective Endocarditis
 - a. 1 major* criterion and 1 minor** criterion; or
 - b. 3 minor** criteria
3. Rejected
 - a. Firm alternate diagnosis explaining evidence of infective endocarditis; or
 - b. Resolution of infective endocarditis syndrome with antibiotic therapy for ≤ 4 days; or
 - c. No pathologic evidence of infective endocarditis at surgery or autopsy, with antibiotic therapy for ≤ 4 days; or
 - d. Does not meet criteria for possible endocarditis, as above

*Duke Major Criteria:

1. Blood culture positive for infective endocarditis
 - a. Typical microorganisms consistent with IE from 2 separate cultures:
 - i. Viridans streptococci, *Streptococcus bovis*, HACEK group, *Staphylococcus aureus*; or
 - ii. Community-acquired enterococci, in the absence of a primary focus, or
 - b. Microorganisms consistent with infective endocarditis from persistently positive blood cultures, defined as follows:
 - i. At least 2 positive cultures of blood samples drawn > 12 hours apart; or
 - ii. All of 3 or a majority of ≥ 4 separate cultures of blood (with first and last sample drawn at least 1 hour apart)
 - c. Single positive blood culture for *Coxiella burnetii* or antiphase I IgG antibody titer $> 1:800$
2. Evidence of endocardial involvement
3. Echocardiogram positive for infective endocarditis (TEE recommended), defined as follows:

- a. Oscillating intracardiac mass on valve or supporting structures, in the path of regurgitant jets, or on implanted material in the absence of an alternative anatomic explanation; or
 - b. Abscess; or
 - c. New partial dehiscence of prosthetic valve
4. New valvular regurgitation (worsening or changing of pre-existing murmur not sufficient)

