****Duke Minor Criteria:**

1. Predisposition, predisposing heart condition or injection drug use
2. Fever, temperature > 38°C
3. Vascular phenomena, major arterial emboli, septic pulmonary infarcts, mycotic aneurysm, intracranial hemorrhage, conjunctival hemorrhages, and Janeway's lesions
4. Immunologic phenomena: glomerulonephritis, Osler's nodes, Roth's spots, and rheumatoid factor
5. Microbiological evidence: positive blood culture but does not meet a major criterion as noted above (excludes single positive cultures for coagulase-negative staphylococci and organisms that do not cause endocarditis) or serological evidence of active infection with organism consistent with infective endocarditis

Endocarditis meeting the Duke definitions for 'definite' or 'possible' will be reported.

Positive blood cultures are not required for the diagnosis of study valve endocarditis. Morbidities associated with active infection, such as valve thrombosis, thrombotic embolus, bleeding event, or paravalvular leak, are included under this category, and not counted in other categories of morbidity.

Hemorrhage

Any episode of major internal or external bleeding that causes death, hospitalization, pericardiocentesis, permanent injury (e.g., vision loss), or requires transfusion will be reported.

Note: A bleeding event is reportable whether or not the subject is taking anticoagulant or antiplatelet medication.

Note: Embolic stroke complicated by bleeding is classified as a neurological event under "embolism" and is not included as a separate bleeding event.

Nonstructural Dysfunction

Any abnormality not intrinsic to the valve itself that results in stenosis or regurgitation of the study valve or hemolysis will be reported. Nonstructural dysfunction refers to problems (exclusive of thrombosis and infection) that do not directly involve valve components yet result in dysfunction of a study valve, as diagnosed by reoperation, autopsy, or clinical investigation.

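### Appendix 11 numbers overlapping endocardial findings as separate Duke major criteria, so a culture-negative dehiscence with a new leak scores as definite endocarditis

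*Combined protocol and SAP*

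**What the plan says.** Appendix 11 defines endocarditis as an infection of the study valve diagnosed by Modified Duke Criteria. The major criteria run in one numbered sequence:

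- Item 1 is a positive blood culture, with detailed sub-items.
- Item 2 reads "Evidence of endocardial involvement" and stops there; nothing defines it.
- Item 3 is "Echocardiogram positive for infective endocarditis (TEE recommended), defined as follows". Its sub-items are an oscillating mass, an abscess, and (3c) "New partial dehiscence of prosthetic valve".
- Item 4 is "New valvular regurgitation (worsening or changing of pre-existing murmur not sufficient").

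The first clinical route to a definite diagnosis is "2 major* criteria; or" one of two alternatives that use minor criteria. One major plus one minor criterion gives a possible diagnosis. Both grades are reported, and the appendix says that positive cultures are not needed.

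Three other provisions matter. A case is rejected if there is a firm alternative explanation (3a), or if surgery or autopsy shows no pathologic evidence and antibiotics were given for 4 days or less (3c). Morbidities tied to an active infection, including "bleeding event, or paravalvular leak, are included under this category, and not counted in other categories of morbidity". Nonstructural dysfunction, where paravalvular leak otherwise belongs, excludes thrombosis and infection.

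Section 5.1 names endocarditis and perivalvular leak separately within the primary safety endpoint. Section 15.1 lists valve dehiscence among the anticipated complications. Section 15.3 and Appendix 11 have the DSMB adjudicate, under the appendix by these same definitions.

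**The concern.** Items 2, 3 and 4 overlap. A positive echocardiogram or a new regurgitant jet is itself evidence that the endocardium is involved, and a partial dehiscence would be expected to leak. The list still numbers them as separate major criteria, and two majors are enough for a definite diagnosis.

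The same finding therefore fits two definitions that exclude each other: an infection, and a device or implant problem that the protocol anticipates. How the items are counted can decide where the event goes. At stake is whether the endocarditis and perivalvular-leak rates mean what their labels say. For a new valve size studied in a single arm, those rates help to describe how the valve performs.

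**Working it through.** The plan states no figure to reproduce. The check applies the Appendix 11 decision rule to an example case.

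**Rule.** Let M be the number of major and m the number of minor criteria met.

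- Definite: M ≥ 2, or M ≥ 1 with m ≥ 3, or m ≥ 5.
- Possible, if not definite: M ≥ 1 with m ≥ 1, or m ≥ 3.
- Otherwise the criteria are not met.

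**Case.** New partial dehiscence (item 3c) with a new leak (item 4) and negative cultures, so item 1 is not met.

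**Readings of items 2 to 4.**

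- A: each item counts. M = 1 + 1 + 1 = 3.
- B: item 2 is an empty heading; items 3 and 4 each count. M = 1 + 1 = 2.
- C: items 2 to 4 are one criterion, counted once. M = 1.

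| Minor criteria met | A (M = 3) | B (M = 2) | C (M = 1) |
|---|---|---|---|
| 0 | definite | definite | not met |
| 1 | definite | definite | possible |
| 2 | definite | definite | possible |
| 3 | definite | definite | definite |

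A and B give the same grade in every row, so the result does not depend on counting the empty item 2. With no minor criterion met, there is no fever and no vascular, immunologic or microbiological sign, yet the case is still definite under both.

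**A single finding** (dehiscence alone, or new leak alone, m = 0). A gives M = 2, definite. B and C give M = 1, not met. Grading one finding as definite thus needs the harshest reading.

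**Effect of a minor criterion.** The first minor criterion is "Predisposition, predisposing heart condition or injection drug use". The documents do not define the term. If a diseased or replaced mitral valve is assumed to satisfy it, then m = 1 and reading C gives possible, which is still reported. Counting items 2 to 4 once would then change the grade but not whether the event appears as endocarditis.

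**The case against.** The strongest reply is that the scoring list is not the whole definition. The category is for infections of the study valve, and a dehiscence known to be sterile is not one. Rejection rule 3a needs neither surgery nor a limit on antibiotics, so it is available for a dehiscence managed without reoperation. The clause that keeps a leak out of other categories covers only morbidities tied to active infection. The DSMB determines event type and, under Section 15.3, may refine the definitions.

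Most of this stands. A reader might infer that any sterile dehiscence with a leak is automatically removed from the leak count. The documents do not support that: if shown to be sterile, it can be rejected and stay under nonstructural dysfunction. Nor does a loss from the thrombosis count follow. A dehiscence with a leak is not a thrombosis, and Appendix 11 keeps a thrombus not caused by infection under valvular thrombosis.

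The reply does not cover the case where infection is neither shown nor excluded. Rule 3a needs a firm alternative. Rule 3c needs surgery or autopsy and a short antibiotic course. The entry condition is itself diagnosed by the Duke list, and Appendix 11 tells the DSMB to adjudicate by it.

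It can also be said that item 2 is naturally a heading, with items 3 and 4 beneath it. The page layout should be checked for that, but items 3 and 4 continue the same 1-to-4 numbering. If only item 2 is treated as a heading, the result is reading B, and the case is still definite.

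**Conclusion.** The printed list can grade a culture-negative dehiscence with a new leak as definite endocarditis with no sign of infection: 2 or 3 majors against a threshold of 2. Counted as one criterion, the same case scores 1 and is at most possible unless three minor criteria are also met.

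The consequence is limited. It arises where infection is neither shown nor excluded and the criteria are counted literally. It can then move an event between the endocarditis and perivalvular-leak components. A first-event analysis of the composite in Section 5.1 would not change, because both are components; a tally of every event could.

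The size of any shift cannot be given. The documents state no planned sample size and no expected rate for either component, so a claim that one or two children would double or erase a rate has no basis in them. The inference that every child meets the predisposition criterion is likewise an assumption, because the term is undefined. The point rests on the printed numbering and scoring rule, which can misclassify a complication that the protocol anticipates.

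**What to change.** Rewrite the major criteria in Appendix 11 so that evidence of endocardial involvement is one criterion, met by a positive echocardiogram (existing sub-items a to c) or by new valvular regurgitation, and counted once however many of these are present.

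Because possible endocarditis is also reported, renumbering alone may leave the event under endocarditis. Tabulate DSMB-adjudicated definite and possible endocarditis on separate lines, so that a reader can see how much of the rate rests on the weaker grade.

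The cost is a short appendix correction and one extra table line. The downside is that some events move from definite to possible. Further rules, such as barring predisposition as the only minor criterion or limiting the not-counted-elsewhere clause to definite infection, would depart from the criteria that the appendix adopts and are not needed here.

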****Duke Minor Criteria:**

1. Predisposition, predisposing heart condition or injection drug use
2. Fever, temperature > 38°C
3. Vascular phenomena, major arterial emboli, septic pulmonary infarcts, mycotic aneurysm, intracranial hemorrhage, conjunctival hemorrhages, and Janeway's lesions
4. Immunologic phenomena: glomerulonephritis, Osler's nodes, Roth's spots, and rheumatoid factor
5. Microbiological evidence: positive blood culture but does not meet a major criterion as noted above (excludes single positive cultures for coagulase-negative staphylococci and organisms that do not cause endocarditis) or serological evidence of active infection with organism consistent with infective endocarditis

Endocarditis meeting the Duke definitions for 'definite' or 'possible' will be reported.

Positive blood cultures are not required for the diagnosis of study valve endocarditis. Morbidities associated with active infection, such as valve thrombosis, thrombotic embolus, bleeding event, or paravalvular leak, are included under this category, and not counted in other categories of morbidity.

Hemorrhage

Any episode of major internal or external bleeding that causes death, hospitalization, pericardiocentesis, permanent injury (e.g., vision loss), or requires transfusion will be reported.

Note: A bleeding event is reportable whether or not the subject is taking anticoagulant or antiplatelet medication.

Note: Embolic stroke complicated by bleeding is classified as a neurological event under "embolism" and is not included as a separate bleeding event.

Nonstructural Dysfunction

Any abnormality not intrinsic to the valve itself that results in stenosis or regurgitation of the study valve or hemolysis will be reported. Nonstructural dysfunction refers to problems (exclusive of thrombosis and infection) that do not directly involve valve components yet result in dysfunction of a study valve, as diagnosed by reoperation, autopsy, or clinical investigation.

Examples of nonstructural dysfunction include: entrapment by pannus, tissue, or suture; paravalvular leak; inappropriate sizing or positioning; residual leak or obstruction after valve implantation or repair; and clinically significant intravascular hemolytic anemia. More than mild recurrent or residual mitral regurgitation after surgical or percutaneous interventional valve procedures (coronary sinus interventions, direct reparative methods, or other methods aimed at achieving ventricular remodeling) is nonstructural dysfunction, unless there is disruption of the valve components themselves, which would then be structural deterioration.

Sudden or progressive dysfunction or deterioration of the study valve may be structural, nonstructural, or both as determined by reoperation, autopsy, or clinical investigation.

Reoperation

Reoperation is any operation that repairs, alters or replaces the study valve. The reasons for reoperation are to be reported and may include reasons other than valve-related morbidity, such as recall, excessive noise, or incidental or prophylactic removal.

Thrombolytic or catheter-aided therapy of valve-related morbidity is not considered reoperation; however, the morbid event that prompted the intervention should be reported.

Structural Valve Deterioration

Dysfunction or deterioration involving the study valve (exclusive of infection or thrombosis), as determined by reoperation, autopsy, or clinical investigation will be reported. Structural valve deterioration refers to changes intrinsic to the valve, such as wear, fracture, poppet escape, calcification, leaflet tear, stent creep, and suture line disruption of components (e.g., leaflets) of the study valve.

Thromboembolism

Any thromboembolic event that occurs in the absence of infection after the immediate perioperative period (when anesthesia-induced unconsciousness is completely reversed) will be reported as valve-related. Thromboembolic events occurring during the procedure will be reviewed and adjudicated by the DSMB to determine if the event is valve or procedure related. Subsets of thromboembolic events are:

Neurologic:

A neurologic thromboembolism is one that results in a central, new neurological deficit, whether temporary or permanent and whether focal or global, that occurs after the subject emerges from anesthesia. Types of neurologic events are:

- Stroke: A prolonged (>72 hours) or permanent neurologic deficit that is usually associated with abnormal results of magnetic resonance imaging or computed tomographic scans. Subjects with minimal, atypical, or protean symptoms that lead to radiographic imaging demonstrating an acute ischemic event are considered to have sustained a stroke.
- Transient Ischemic Attack (TIA): Fully reversible symptoms of short duration. If radiographic imaging demonstrates an acute central neurologic lesion (“cerebral infarction with transient symptoms”), however, such subjects are reclassified as having sustained a stroke.

Noncerebral:

A thromboembolism documented operatively, at autopsy, or clinically that produces signs or symptoms attributable to complete or partial obstruction of a peripheral artery.

Valvular Thrombosis

Any thrombus not caused by infection attached to or near the study valve that occludes part of the blood flow path, interferes with valve function, or is sufficiently large to warrant treatment. Valvular thrombosis found at autopsy in a subject whose cause of death was not valve related or found at operation for an unrelated indication should also be counted as valvular thrombosis.
